### 10.2.2 Renal safety monitoring

The following categories of abnormal renal laboratory values have to be considered during the course of the study:

- Serum creatinine increase  $\geq 25\%$  compared to baseline during normal hydration status
- Urine protein-creatinine ratio (PCR)  $\geq 1\text{g/g}$  or  $\geq 100\text{ mg/mmol}$ , OR new onset dipstick proteinuria  $\geq 3+$  OR new onset dipstick hematuria  $\geq 3+$  (after excluding menstruation, UTI, extreme exercise, or trauma)

Abnormal renal event findings must be confirmed after  $\leq 5$  days after first notification of the result.

Every renal laboratory trigger or renal event as defined in [Table 16-3](#) should be followed up by the investigator or designated personnel at the trial site as summarized in Appendix 3 ([Section 16.3](#)). Please also see Section 10 (Appendix 4) of the Site Operations Manual for further guidance.

\*Please see [Section 9.1.1](#) for maximum duration of study drug interruption permitted.

## 11 Data Collection and Database management

### 11.1 Data collection

Designated investigator staff will enter the data required by the protocol into the Electronic Case Report Forms (eCRF). The eCRFs have been built using fully validated secure web-enabled software that conforms to 21 CFR Part 11 requirements. Investigator site staff will not be given access to the EDC system until they have been trained. Automatic validation programs check for data discrepancies in the eCRFs, allow modification and/or verification of the entered data by the investigator staff.

The investigator/designee is responsible for assuring that the data entered into the eCRF is complete, accurate, and that entry and updates are performed in a timely manner. The Investigator must certify that the data entered are complete and accurate.

After final database lock, the investigator will receive copies of the subject data for archiving at the investigational site.

All data should be recorded, handled, and stored in a way that allows its accurate reporting, interpretation, and verification.

### 11.2 Database management and quality control

Novartis personnel will review the data entered by investigational staff for completeness and accuracy. Electronic data queries stating the nature of the problem and requesting clarification will be created for discrepancies and missing values and sent to the investigational site via the EDC system. Designated investigator site staff are required to respond promptly to queries and to make any necessary changes to the data.

Concomitant treatments and prior medications entered into the database will be coded using the World Health Organization (WHO) Drug Reference List, which employs the Anatomical Therapeutic Chemical classification system. Medical history/current medical conditions and

adverse events will be coded using the Medical Dictionary for Regulatory Activities (MedDRA) terminology.

Randomization codes and data about all study treatment (s) dispensed to the subject and all dosage changes will be tracked using an Interactive Response Technology (IRT). The system will be supplied by a vendor, who will also manage the database. The data will be sent electronically to Novartis at specific timelines.

Each occurrence of a code break via IRT will be reported to the clinical team and monitor. The code break functionality will remain available until study shut down or upon request of Novartis.

Once all the necessary actions have been completed and the database has been declared to be complete and accurate, it will be locked **and the treatment codes will be unblinded** and made available for data analysis. Any changes to the database after that time can only be made after written agreement by Novartis management.

### **11.3 Site monitoring**

Before study initiation, at a site initiation visit or at an investigator's meeting, a Novartis representative will review the protocol and data capture requirements with the investigators and their staff. During the study, Novartis employs several methods of ensuring protocol and GCP compliance and the quality/integrity of the sites' data. The field monitor will visit the site to check the completeness of subject records, the accuracy of data capture / data entry, the adherence to the protocol and to Good Clinical Practice, the progress of enrollment, and to ensure that study treatment is being stored, dispensed, and accounted for according to specifications. Key study personnel must be available to assist the field monitor during these visits. Continuous remote monitoring of each site's data may be performed by a centralized Novartis CRA organization. Additionally, a central analytics organization may analyze data & identify risks & trends for site operational parameters, and provide reports to Novartis clinical teams to assist with trial oversight.

The investigator must maintain source documents for each subject in the study, consisting of case and visit notes (hospital or clinic medical records) containing demographic and medical information, laboratory data, electrocardiograms, and the results of any other tests or assessments. All information on CRFs must be traceable to these source documents in the subject's file. The investigator must also keep the original informed consent form signed by the subject (a signed copy is given to the subject).

The investigator must give the monitor access to all relevant source documents to confirm their consistency with the data capture and/or data entry. Novartis monitoring standards require full verification for the presence of informed consent, adherence to the inclusion/exclusion criteria, documentation of SAEs, and of data that will be used for all primary variables. Additional checks of the consistency of the source data with the CRFs are performed according to the study-specific monitoring plan. No information in source documents about the identity of the subjects will be disclosed.

## 12 Data analysis and statistical methods

Any data analysis carried out independently by the investigator should be submitted to Novartis before publication or presentation.

### 12.1 Analysis sets

For all analysis sets, subjects will be analyzed according to the study treatment(s) received.

The safety set (SAF) will include all subjects who received at least one dose of study drug whether or not being randomized. The safety set will be used in the analysis of all safety variables.

The PD analysis set will include all subjects with available PD data and no protocol deviations with relevant impact on PD data.

The PK analysis set will include all subjects with at least one available valid (i.e. not flagged for exclusion) PK concentration measurement, who received any study drug and with no protocol deviations that impact on PK data.

### 12.2 Subject demographics and other baseline characteristics

Demographic and other baseline data including medical history, respiratory history, PRO data and current medical conditions present before signing the informed consent will be listed and summarized descriptively by treatment group for the Safety set.

Categorical data will be presented as frequencies and percentages. For continuous data, mean, standard deviation, median, minimum, and maximum will be presented.

Relevant medical histories and current medical conditions at baseline will be summarized by system organ class and preferred term, by treatment group.

### 12.3 Treatments

The Safety set will be used for the analyses below. Categorical data will be summarized as frequencies and percentages. For continuous data, mean, standard deviation, median, minimum, and maximum will be presented.

The concentration data will be summarized by means of descriptive statistics using the safety set.

Concomitant medications and significant non-drug therapies prior to and after the start of the study treatment will be listed and summarized according to the Anatomical Therapeutic Chemical (ATC) classification system, by treatment group.

### 12.4 Analysis of the primary endpoint(s)

Commercially Confidential Information

---

Commercially Confidential Information

#### **12.4.1 Definition of primary endpoint(s)**

The primary variable of the study is the change from baseline in sputum eosinophil percentage at week 6. As sputum eosinophil percentage has been found to follow a log-normal distribution, the analysis will be based on log10-transformed scale. The baseline measurement is defined as sputum eosinophil percentage prior to the first dosing (on log10-transformed scale).

#### **12.4.2 Statistical model, hypothesis, and method of analysis**

The treatment effect of the primary variable will be analyzed using a Bayesian model

Commercially Confidential Information

### **12.4.3 Handling of missing values/censoring/discontinuations**

Induced sputum, from which the primary endpoint is derived, is collected only once post-treatment (at 6 weeks). Only trial completers will be included in the statistical model. Handling of missing values is not planned.

For other endpoints that are collected in multiple time points CCI the repeated measures analysis includes all available information in terms of measurements at all times. If missing measurements are missing at random, an analysis of the available data provides consistent estimates of model parameters.

### **12.4.4 Sensitivity and Supportive analyses**

#### **12.4.4.1 Sensitivity analysis**

The same Bayesian model stated in [Section 12.4.2](#) will be repeated

Commercially Confidential Information

#### **12.4.4.2 Supportive analysis**

The proportion and timing of starting concomitant systemic steroids will be summarized and compared between treatment groups as the supplemental estimate of the primary estimand using safety data set.

## **12.5 Analysis of secondary endpoints**

### **12.5.1 Safety endpoints**

Safety summaries (tables, figures) include only data from the on-treatment period with the exception of baseline data which will also be summarized where appropriate (e.g. change from baseline summaries). In addition, a separate summary for death including on treatment and post treatment deaths will be provided. In particular, summary tables for adverse events (AEs) will summarize only on-treatment events, with a start date during the on-treatment period (treatment-emergent AEs).

#### **Adverse events**

All information obtained on adverse events will be displayed by treatment group and subject.

The number (and percentage) of subjects with treatment emergent adverse events (events started after the first dose of study medication or events present prior to start of treatment but increased in severity based on preferred term) will be summarized in the following ways:

- by treatment, primary system organ class and preferred term.
- by treatment, primary system organ class, preferred term and maximum severity.
- by treatment, Standardized MedDRA Query (SMQ) and preferred term.

Separate summaries will be provided for study medication related adverse events, death, serious adverse events, and other significant adverse events leading to discontinuation.

The number and proportion of subjects with adverse events of special interest will be summarized by treatment group

A subject with multiple adverse events within a primary system organ class is only counted once towards the total of the primary system organ class.

## **Vital signs**

Vital signs (i.e. blood pressure and pulse rate) will be summarized with standard descriptive statistics of raw data and changes from baseline for each visit separately. The numbers of subjects with vital signs meeting the definition of notably abnormal will be presented by parameter.

## **ECG**

1. PR, QRS, QT, QTcF, and RR intervals will be obtained from ECGs for each subject during the study. ECG data will be read and interpreted locally.
2. Categorical Analysis of QT/QTc interval data based on the number of subjects meeting or exceeding predefined limits in terms of absolute QT/QTc intervals or changes from baseline will be presented. In addition, a listing of these subjects will be produced (by treatment group).

All ECG data will be listed by treatment group, subject and visit/time, abnormalities will be flagged. Summary statistics will be provided by treatment and visit/time.

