- Barrier methods of contraception: Condom or Occlusive cap (diaphragm or cervical/vault caps) if allowed as effective method of contraception by local regulations. For United Kingdom: with spermicidal foam/gel/film/cream/ vaginal suppository.
- Use of oral, (estrogen and progesterone), injected or implanted hormonal methods of contraception or other forms of hormonal contraception that have comparable efficacy (failure rate <1%), for example hormone vaginal ring or transdermal hormone contraception or placement of an intrauterine device (IUD) or intrauterine system (IUS).

In case of use of oral contraception women should have been stable on the same pill for a minimum of 3 months before taking investigational drug.

Women are considered post-menopausal and not of child bearing potential if they have had 12 months of natural (spontaneous) amenorrhea with an appropriate clinical profile (e.g. age appropriate, history of vasomotor symptoms) or have had surgical bilateral oophorectomy (with or without hysterectomy), total hysterectomy or tubal ligation at least six weeks ago. In the case of oophorectomy alone, only when the reproductive status of the woman has been confirmed by follow up hormone level assessment is she considered not of child bearing potential.

If local regulations deviate from the contraception methods listed above to prevent pregnancy, local regulations apply and will be described in the ICF.

9. Patients with any of the following cardiac related concerns:

- A resting QTcF (Fridericia)  $\geq 450$  msec (male) or  $\geq 460$  msec (female) at screening or baseline visit.
- A history of familial long QT syndrome or known family history of Torsades de Pointes.
- Receiving any medications or other agents known to prolong the QT interval.
- Patients with a history of moderate or severe uncontrolled tachyarrhythmias.
- History of a clinically significant cardiovascular event within 1 year prior to the screening visit, such as acute myocardial infarction, congestive heart failure, unstable arrhythmias.
- Patients who, in the judgment of the investigator have a clinically significant ECG abnormality such as (but not limited to) sustained ventricular tachycardia, or clinically significant second or third degree AV block without a pacemaker.

10. Patients on any statin therapy with a CK level  $> 2 \times$  ULN at screening or baseline visit.

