#### **8.4.2      Electrocardiogram (ECG)**

Full details of all procedures relating to the ECG collection and reporting are contained in the Site Operations Manual.

PR interval, QRS duration, heart rate, RR interval, QT interval, QTcF

The Fridericia QT correction formula (QTcF) must be used for clinical decisions.

Unless auto-calculated by the ECG machine, the investigator must calculate QTcF at the Screening visit to assess eligibility. See the Site Operations Manual for additional details.

Clinically significant abnormalities must be reported as adverse events. See [Section 16.1](#) for notable QTc values and action.

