## 16 Appendices

### 16.1 Appendix 1: Clinically notable laboratory values

The central laboratory will flag laboratory values falling outside of the normal ranges on the central laboratory reports. Investigators are responsible for reviewing these abnormal values for clinical significance, signing the laboratory reports to indicate their review, and reporting values considered clinically significant in the appropriate eCRF.

Any clinically significant abnormal laboratory value should be evaluated and followed-up by the investigator until normal or a cause for the abnormality is determined.

See [Section 16.2](#) for specific liver event and laboratory test trigger definitions and follow-up requirements.

For ECGs, a notable QTc value is defined as a QTcF (Fridericia) interval of  $\geq 450$  msec for males or  $\geq 460$  msec for females – all such ECGs will require assessment for clinical relevance and continuance of the subject by the Investigator in consultation with Novartis.

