## ECG evaluations

All ECG data will be listed by treatment, subject and visit/time, abnormalities will be flagged. Summary statistics will be provided by treatment and visit/time.

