**Table 7-2 Reference ranges for ECGs**

Variable	Type of abnormality	Criterion
PR duration (msec)	High	> 200 msec
QRS duration (msec)	High	≥ 120 msec
QTcF (females) (msec)	High	> 460 msec
QTcF (males) (msec)	High	> 450 msec
Heart rate (bpm)	High	> 100 msec
	Low	<40 bpm

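### The SAP flags QTcF only strictly above 450/460 msec, while protocol Appendix 1 calls it notable at or above those values, so an ECG exactly at the limit is listed without a flag

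*Protocol*

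**What the plan says.** **Protocol, Appendix 1 (16.1).** The text states that "a notable QTc value is defined as a QTcF (Fridericia) interval of" at least 450 msec for males or at least 460 msec for females. The investigator, in consultation with the sponsor, must assess every such ECG. Section 8.4.2 sends the reader to 16.1 "for notable QTc values and action".

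**Protocol, 5.2.** The cardiac exclusion criterion applies the same two figures, again inclusively, at screening or baseline.

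**Protocol, 12.5.1, ECG.** A categorical QT/QTc analysis is planned, based on "the number of subjects meeting or exceeding predefined limits in terms of absolute QT/QTc intervals or changes from baseline", together with a listing of the subjects concerned. The wording is inclusive, but the section gives no number and does not cite Appendix 1.

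**SAP, 7.2, ECG evaluations.** The SAP states: "All ECG data will be listed by treatment, subject and visit/time, abnormalities will be flagged". Summary statistics by treatment and visit/time are also planned. The criteria follow under "Table 7-2 Reference ranges for ECGs". The QTcF rows read strictly greater than 450 msec for males and strictly greater than 460 msec for females. The QRS row of the same table reads at or above 120 msec.

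**The concern.** The two documents use the same cut-points with different operators. SAP 1.1 says the SAP implements the analysis planned in the protocol, so a shifted boundary should be either deliberate and explained or corrected. No explanation is visible.

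ECG intervals are part of the secondary safety endpoint. What is at stake is traceability. Someone who compares the flagged QTcF values in the report with the ECGs that Appendix 1 treats as notable could find that they differ, with no documented reason. The difference always runs one way: the SAP flags the same number or fewer.

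**Working it through.** The plan has no figure of its own on this point to reproduce. The check has two parts: the rules at the boundary, and the likely frequency of a boundary value.

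**1. The rules at the boundary**

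| Sex | QTcF (msec) | Protocol 16.1 (at or above) | SAP 7.2 table (strictly above) |
|---|---|---|---|
| Male | 449 | not notable | not flagged |
| Male | 450 | notable | not flagged |
| Male | 451 | notable | flagged |
| Female | 459 | not notable | not flagged |
| Female | 460 | notable | not flagged |
| Female | 461 | notable | flagged |

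The rules differ only at exact equality. The inclusive sign in the QRS row shows that this character survived conversion from PDF, so the strict sign in the QTcF rows is unlikely to be a reading artefact.

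**2. How often a value falls exactly on the limit**

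The documents give no QTcF distribution and no recording precision, so the following are assumptions: QTcF is normal, recorded to the whole millisecond, with mean d msec below the sex-specific limit (d = 25, 35, 45) and SD s (15, 20, 25 msec). The planned 50 subjects come from protocol 12.8.1.

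- Probability of exactly the limit: p = Φ((d + 0.5)/s) − Φ((d − 0.5)/s)
- Probability of at or above the limit: q = 1 − Φ((d − 0.5)/s)
- Expected ECGs on the limit per time point: 50 × p

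Central case, d = 35 and s = 20: p = Φ(1.775) − Φ(1.725) = 0.9621 − 0.9577 = 0.0043 after rounding the unrounded difference. Then 50 × 0.0043 ≈ 0.2. With q = 0.0423, the share p/q is 0.102.

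| d | s | p | 50 × p | p/q |
|---|---|---|---|---|
| 25 | 15 | 0.0066 | 0.33 | 0.130 |
| 25 | 20 | 0.0091 | 0.46 | 0.083 |
| 25 | 25 | 0.0097 | 0.48 | 0.059 |
| 35 | 15 | 0.0017 | 0.09 | 0.163 |
| 35 | 20 | 0.0043 | 0.22 | 0.102 |
| 35 | 25 | 0.0060 | 0.30 | 0.072 |
| 45 | 15 | 0.0003 | 0.015 | 0.197 |
| 45 | 20 | 0.0016 | 0.08 | 0.122 |
| 45 | 25 | 0.0032 | 0.16 | 0.084 |

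So p runs from about 0.0003 to 0.010, which is about 0.015 to 0.5 ECGs per time point for 50 subjects. The share p/q runs from 6% to 20%, but it is highest where the tail is thinnest. At d = 45 and s = 15, the 20% is a share of only 0.15% of ECGs. The absolute figure is the one to use.

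**The case against.** The case against giving this much weight is strong, and most of it stands.

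- **No ECG is lost.** Every ECG is listed by subject and visit, so a value of 450 msec is printed, only without a flag. The Appendix 1 review takes place during the trial, between investigator and sponsor, and does not depend on SAP flags. A reader might infer that notable ECGs go unreviewed; the documents do not support that.
- **An error in the categorical count is not shown.** A reader might infer that the count in protocol 12.5.1 will be too low. That section prints no limits, covers QT and changes from baseline as well as absolute QTc, and does not refer to Appendix 1. The visible SAP text uses its table for flagging and does not tie it to any count. Parts of the SAP safety section are redacted, so the limits for the count may be stated there.
- **Starting below the limit proves little.** The entry criterion means that enrolled subjects begin below the limit. It is tempting to conclude that the limit itself is the first notable value each would reach. QTcF can move from 435 to 457 msec between visits without ever being recorded as 450.
- **The effect may be smaller still.** If QTcF is stored with decimals, exact equality is very rare. SAP section 2 records early termination, so the planned 50 may not have been reached; the documents do not give the actual number.
- **The cause may be a version lag.** SAP 1.2 bases the SAP on protocol v01 of 08Apr2019, while the protocol contents list a later Amendment 2. The operator in v01 cannot be seen. This might explain the mismatch with the current text, but does not remove it.

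What survives is the mismatch between Appendix 1 and the SAP table, which needs no inference about 12.5.1.

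**Conclusion.** The point holds as a small inconsistency in an analysis flag. At exactly 450 msec (males) or 460 msec (females), the protocol calls the ECG notable and the SAP leaves it unflagged; at every other value the two agree. Under the stated assumptions, fewer than one ECG per time point is expected to be affected in 50 subjects. Those figures rest on assumed normality, mean, SD and whole-millisecond recording, none of which the documents give. An effect on the 12.5.1 count is possible but conditional on where its limits come from. This is a minor correction, worth making because it costs almost nothing and concerns a named secondary safety endpoint.

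**What to change.** In the ECG reference-range table of SAP 7.2, change the operator in the two QTcF rows to at or above (450 msec males, 460 msec females), so that the analysis flag matches the protocol's own Appendix 1 definition. No clinical threshold or review rule changes.

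Add one sentence to the SAP stating that the absolute-QTcF part of the 12.5.1 categorical analysis uses these same limits. The operator change alone does not settle 12.5.1, which also calls for change-from-baseline limits and a listing of the subjects who meet them. If the redacted SAP text does not already give these, they should be named in the same place.

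The cost is two symbols and a sentence in the SAP, and one condition in the flagging program.
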